4.3 Interim analyses and data monitoring

When PS0010 is unblinded, Sponsor study team members from PS0011 with access to the PS0010 data will be unblinded. However, subjects and investigators will remain blinded. This operational unblinding to PS0011 treatment assignment will pertain to selected clinical PS0010 study team members (some of whom may be involved in PS0011). PS0010 and PS0011 will have the same blinded programming teams for reporting and will remain blinded to PS0010 and PS0011 treatment assignment. An independent programming team will be used for the final unblinding for PS0010 reporting.

A Data Monitoring Committee (DMC) will review the safety data on a recurring basis as outlined in the DMC charter. The outputs reviewed by the DMC will include the accrued data from both PS0010 and PS0011, allowing for summaries of the combined data across the studies. The details of the outputs to be prepared are described in a separate DMC SAP.

An interim analysis focusing on PS0011 only will take place once all subjects have completed the Week 48 visit, but not including the SFU visit. The Clinical Study Report will be updated at a later date in order to incorporate the SFU data once available.

4.4 Multicenter studies

This is a multicenter study with sites in Europe, Canada, Japan and USA.

4.5 Multiple comparisons/multiplicity

Not applicable.

4.6 Active-control studies intended to show equivalence

Not applicable.

4.7 Examination of subgroups

Subgroup analyses will be performed on the secondary efficacy variables.

The following subgroup analyses will be performed:

- Age (<65 years, ≥65 years)
- Gender (male, female)
- Duration of disease at PS0010 Baseline (<median, ≥median)
- Region (North America [Canada, USA], Europe and Asia [Czech Republic, Hungary, Poland, Japan])
- Body weight at PS0010 Baseline (<100 kg, ≥100 kg)
- Body Mass Index (BMI) at PS0010 Baseline (<25 kg/m², 25 to <30 kg/m², ≥30 kg/m²)
- Prior biologic systemic therapy at PS0010 Baseline (yes, no)

- Prior anti-TNF therapy at PS0010 Baseline (yes, no)
- Any prior systemic therapy at PS0010 Baseline (yes, no)
- Anti-bimekizumab antibody positivity at any time on treatment during PS0010 or PS0011 (yes, no)
- PASI score at PS0010 baseline (<20, ≥20)
- Psoriasis BSA at PS0010 baseline (<20%, ≥20%).

These summaries, using the FAS, will be based on imputed data (NRI) and will include descriptive statistics only. If there are less than 2 subjects in any subgroup category/treatment group, then that subgroup category will not be summarized. If it is possible to collapse subgroups with more than 2 categories, then collapsing may be done to get categories with no less than 2 subjects per subgroup category/treatment group.

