5.2 Schedule of study assessments

A schedule of study assessments is presented in [Table 5–1](#).

REDACTED COPY
This document cannot be used to support any marketing authorization application and any extensions or variations thereof.

Table 5–1: Schedule of study assessments

Protocol activity	Visit Week ^a	Treatment Period													SFU ^b
	PS0011 Baseline	Wk 4	Wk 8	Wk 12	Wk 16	Wk 20	Wk 24	Wk 28	Wk 32	Wk 36	Wk 40	Wk 44	Wk 48/WD		
Informed consent	X ^c														
Inclusion/exclusion	X ^d														
Physical exam ^e	X ^f												X	X	
Body weight	X ^f												X	X	
Vital signs ^g	X ^f	X	X	X	X	X	X	X	X	X	X	X	X	X	
Hematology/biochemistry	X ^f	X	X	X	X	X	X	X	X	X	X	X	X	X	
Urinalysis	X ^f			X			X			X			X	X	
12-lead ECG	X ^f						X						X	X	
Pregnancy testing ^h	X ^f	X	X	X	X	X	X	X	X	X	X	X	X	X	
eC-SSRS	X ^f	X	X	X	X	X	X	X	X	X	X	X	X	X	
IGRA TB test ⁱ	j												X		
TB questionnaire	X ^f			X			X			X			X		
Blood sample for bimekizumab plasma concentrations ^k	X ^f	X	X	X	X			X			X		X	X	
Blood sample for anti-bimekizumab antibodies ^k	X ^f	X	X	X	X			X			X		X	X	
PASI	X ^f	X	X	X	X	X	X	X	X	X	X	X	X	X	
IGA	X ^f	X	X	X	X	X	X	X	X	X	X	X	X	X	
DLQI	X ^f	X		X			X			X			X		
BSA	X ^f	X	X	X	X	X	X	X	X	X	X	X	X		
mNAPSI	X ^f	X		X			X			X			X		
PSSI	X ^f	X		X			X			X			X		
PGADA	X ^f			X			X			X			X		
SF-36	X ^f			X			X			X			X		

Table 5–1: Schedule of study assessments

Protocol activity	Visit Week ^a PS0011 Baseline	Treatment Period												SFU ^b
		Wk 4	Wk 8	Wk 12	Wk 16	Wk 20	Wk 24	Wk 28	Wk 32	Wk 36	Wk 40	Wk 44	Wk 48/ WD	
HADS	X ^f	X	X	X	X	X	X	X	X	X	X	X	X	X
Concomitant medications	X	X	X	X	X	X	X	X	X	X	X	X	X	X
Adverse events	X	X	X	X	X	X	X	X	X	X	X	X	X	X ^l
IXRS	X	X	X	X	X	X	X	X	X	X	X	X	X	X
Bimekizumab administration ^m	X	X	X	X ^m	X ^m	X ^m	X ^m	X ^m	X ^m	X ^m	X ^m	X ^m	X ^m	

BSA=body surface area; DLQI=Dermatology Life Quality Index; ECG=electrocardiogram; eC-SSRS=electronic Columbia-Suicide Severity Rating Scale; HADS=Hospital Anxiety and Depression Scale; IGA=Investigator’s Global Assessment; IGRA=interferon gamma release assay; IXRS=interactive voice or web response system; mNAPSI=modified Nail Psoriasis Severity Index; PASI=Psoriasis Area and Severity Index; PGADA=Patient’s Global Assessment of Disease Activity; PSSI=Psoriasis Scalp Severity Index; Q4W=every 4 weeks; SF-36=36-item Short Form Health Survey; SFU=Safety Follow-Up; TB=tuberculosis; WD=withdrawal; Wk=week

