^a Visit windows of ±3 days from the first dose (Baseline) at all visits except SFU, which has a window of -3 and +7 days from scheduled visit date.

^b The SFU Visit will occur 20 weeks after the last dose of bimekizumab or placebo.

^c Ensure that the informed consent for PS0011 was completed by the subject during the Week 8 or Week 12 Visit of PS0010 (must be done before any study assessments are performed for PS0011).

^d To be performed prior to the first dose of bimekizumab or placebo in PS0011.

^e Includes evaluation of signs and symptoms of active TB and risk for exposure to TB.

^f The noted PS0011 Baseline assessments will be obtained at the Week 12 Visit of PS0010 and do not need to be recorded on the case report form for this study.

^g Vital signs (blood pressure, pulse rate, and temperature) are to be measured prior to blood sampling and prior to dosing, where applicable.

^h Pregnancy testing will be urine testing at all visits except SFU, which will be a serum test.

ⁱ It is recommended that the QuantiFERON TB GOLD test be performed.

^j Ensure that an IGRA test was performed during the Week 8 Visit of PS0010 and the result was negative.

^k All blood samples are to be taken prior to dosing.

^l Including assessment for the development of different forms of psoriasis at the SFU visit.

^m Subjects who received placebo or bimekizumab 64mg, 160mg, or 320mg loading dose + 160mg Q4W in PS0010 must achieve PASI90 response at Week 12 in PS0010 to enter the PS0011 extension study on the same treatment dose. Subjects who do not achieve PASI90 response at Week 12 in PS0010 while receiving placebo or bimekizumab 64mg will be assigned to receive bimekizumab 160mg on entering PS0011. Subjects who do not achieve PASI90 response at Week 12 in PS0010 while receiving bimekizumab 160mg or 320mg loading dose + 160mg will be assigned to receive bimekizumab 320mg Q4W on entering PS0011. Subjects who receive bimekizumab 320mg or 480mg Q4W in PS0010 will be assigned to receive bimekizumab 320mg Q4W on entering PS0011, regardless of their PASI90 response at Week 12 in PS0010. Any subject who does not achieve PASI75 response at Week 12 or later in PS0011 will be withdrawn from study treatment and will return to complete the Early Withdrawal Visit assessments.

[figure not shown]

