8.2 Week 4 (±3 days)

All procedures or assessments will be performed prior to administration of study drug, unless otherwise noted. The following procedures or assessments will be performed:

- Vital signs (blood pressure, pulse rate, and temperature)
- eC-SSRS
- PASI
- IGA

-
- DLQI
 - BSA
 - mNAPSI
 - PSSI
 - HADS
 - Obtain blood samples for:
 - Standard safety laboratory tests (hematology and biochemistry)
 - Bimekizumab plasma concentration
 - Anti-bimekizumab antibodies
 - Obtain urine sample for:
 - Urine pregnancy test for women of childbearing potential
 - Concomitant medications
 - Record AEs
 - Contact the IXRS
 - Study medication administration (after all other visit assessments are completed)

8.3 Week 8 (± 3 days); Week 16 (± 3 days); Week 32 (± 3 days); and Week 40 (± 3 days)

All procedures or assessments will be performed prior to administration of study drug (if applicable), unless otherwise noted. The following procedures or assessments will be performed:

- Vital signs (blood pressure, pulse rate, and temperature)
- eC-SSRS
- PASI
- IGA
- BSA
- HADS
- Obtain blood samples for:
 - Standard safety laboratory tests (hematology and biochemistry)
 - Bimekizumab plasma concentration (not collected at Week 32)
 - Anti-bimekizumab antibodies (not collected at Week 32)
- Obtain urine sample for:
 - Urine pregnancy test for women of childbearing potential

-
- Concomitant medications
 - Record AEs
 - Contact the IXRS
 - Study medication administration (after all other visit assessments are completed)

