8.4 Week 12 (± 3 days)

The following procedures or assessments will be performed prior to administration of study drug (if applicable):

- Vital signs (blood pressure, pulse rate, and temperature)
- eC-SSRS
- TB questionnaire
- PASI
- IGA
- DLQI
- BSA
- mNAPSI
- PSSI
- PGADA
- SF-36
- HADS
- Obtain blood samples for:
 - Standard safety laboratory tests (hematology and biochemistry)
 - Bimekizumab plasma concentration
 - Anti-bimekizumab antibodies
- Obtain urine sample for:
 - Standard safety laboratory tests (urinalysis)
 - Urine pregnancy test for women of childbearing potential
- Concomitant medications
- Record AEs
- Contact the IXRS
- Study medication administration (after all other visit assessments are completed)

8.5 Week 20 (± 3 days); Week 28 (± 3 days); and Week 44 (± 3 days)

The following procedures or assessments will be performed prior to administration of study drug (if applicable):

- Vital signs (blood pressure, pulse rate, and temperature)
- eC-SSRS
- PASI
- IGA
- BSA
- HADS
- Obtain blood samples for:
 - Standard safety laboratory tests (hematology and biochemistry)
 - Bimekizumab plasma concentration (collected only at Week 28)
 - Anti-bimekizumab antibodies (collected only at Week 28)
- Obtain urine sample for:
 - Urine pregnancy test for women of childbearing potential
- Concomitant medications
- Record AEs
- Contact the IXRS
- Study medication administration (after all other visit assessments are completed)

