4.2.2 Handling missing data for the efficacy analyses

For the planned efficacy analysis, missing responder data will be imputed using non-responder imputation (NRI). That is, subjects that discontinue study medication early or who have missing data at a given time point will be counted as non-responders. Summaries based on observed case data will also be prepared.

Continuous efficacy variables will be imputed using multiple imputation (MI) via the Markov-Chain Monte Carlo (MCMC) method. Summaries based on observed case data will also be prepared.

The MI procedure for continuous efficacy variables (based on MCMC) will be applied as follows:

1. Create a dataset, one for each treatment group, of subjects with observed values and those needing estimation by multiple imputation. The missing values in each dataset will be filled in using the MCMC method with a total of 100 sets of imputations being performed. Values at Baseline and at each post-Baseline visit will be included in the imputation model in chronological order with prior biologic exposure and region as factors. The resulting datasets for each treatment arm will be combined into one complete dataset based on each of the 100 imputations.

Note: The imputation model based on the MCMC method will only allow continuous variables in the imputation model. Therefore, prior biologic exposure and region will be re-coded as indicator variables (with values of 0 or 1 for each level of the variable). In order to achieve model convergence, prior biological exposure may be dropped from the model, if convergence is still not obtained then region may also be dropped from the model.

2. The relevant change from Baseline (or percent change from Baseline) values will then be derived based on the imputed datasets and will be summarized by imputation.
3. The summary statistics from each of the 100 imputed datasets will be combined for the calculation of means and standard deviations using Rubin's rules, which account for the uncertainty associated with the imputed values (Rubin, 1987). This will be done using SAS PROC MIANALYZE. For calculation of other descriptive statistics such as the median, min and max, Rubin's rules do not apply. Multiple imputation estimates will be computed by simply averaging the estimates from the $m = 1, \dots, M$ independent repetitions of the imputation algorithm:

$$\bar{\theta} = \frac{1}{M} \sum_{m=1}^M \hat{\theta}_m$$

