9.2 Immunogenicity

9.2.1 Anti-bimekizumab antibodies

Subjects with a positive on-treatment (i.e., excluding PS0010 Baseline) anti-BKZ antibody result in either PS0010 or PS0011 will be classified as anti-BKZ positive.

Anti-BKZ antibody status will be summarized for each PS0010/PS0011 treatment group at each scheduled PS0010 and PS0011 visit using the PK-PPS analysis set. The first occurrence of anti-BKZ antibody positivity will also be presented for each PS0010/PS0011 treatment group at each scheduled PS0010 and PS0011 visit.

The anti-BKZ antibody status will be determined for each visit where samples are taken for drug concentration means. The cut point for determining whether the anti-bimekizumab antibody level is sufficiently high to be considered anti-BKZ antibody positive is not yet known. However, this will be determined prior to the database lock of the PK and anti-BKZ antibody data.

A line plot of the percentage of anti-BKZ antibody positive subjects at each visit will be produced by PS0010/PS0011 treatment group. All individual subject-level anti-BKZ antibody results will be listed.

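### The efficacy subgroup by antibody status uses positivity at any time, so it depends on length of follow-up and favours antibody-positive subjects if seroconversion continues after Week 12

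*SAP*

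**What the plan says.** SAP 4.7 states: "Subgroup analyses will be performed on the secondary efficacy variables". These variables are PASI90 and IGA response over time. One of the twelve splits is "Anti-bimekizumab antibody positivity at any time on treatment during PS0010 or PS0011 (yes, no". The summaries use the Full Analysis Set (FAS) with NRI and are descriptive only.

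SAP 9.2.1 makes a single positive result enough: "Subjects with a positive on-treatment (i.e., excluding PS0010 Baseline) anti-BKZ antibody result in either PS0010 or PS0011 will be classified as anti-BKZ positive". Only the PS0010 Baseline is named as excluded. Whether a sample from the Safety Follow-Up (SFU) visit counts as on treatment is not stated.

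SAP 4.2.2 sets the missing-data rule: "subjects that discontinue study medication early or who have missing data at a given time point will be counted as non-responders".

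Protocol 5.1 and 6.3 (criterion 12) withdraw any subject who does not reach PASI75 at Week 12 or later in PS0011. Protocol 8.10 gives that subject an Early Withdrawal visit with the Week 48 assessments, which include an antibody sample. SAP 3.3 keeps that sample and maps it to the next antibody visit.

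The Table 5-1 row "Blood sample for anti-bimekizumab antibodies" marks PS0011 Baseline, Weeks 4, 8, 12, 16, 28, 40, 48/withdrawal and SFU. Protocol 8.3 and 8.5 agree: "Anti-bimekizumab antibodies (not collected at Week 32") and "Anti-bimekizumab antibodies (collected only at Week 28"). The PS0011 Baseline sample is the PS0010 Week 12 sample; Table 5-1 notes that "The noted PS0011 Baseline assessments will be obtained at the Week 12 Visit of PS0010".

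**The concern.** The other splits in SAP 4.7 are fixed baseline or demographic characteristics. This one is decided during follow-up, with no landmark, so a Week 8 response can be sorted by a Week 48 antibody result.

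Follow-up in turn depends on response. Failing PASI75 does two things to a subject: it makes the subject a non-responder at every later visit, and it ends the routine antibody sampling. Subjects who fail early therefore have fewer chances to be found positive and tend to collect in the antibody-negative group. This is a form of immortal-time bias.

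Immunogenicity is a stated objective (Protocol 3.3), and the SAP plans no other efficacy summary by antibody status. The bias runs towards reassurance, which is the unhelpful direction when the question is whether antibodies reduce efficacy.

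**Working it through.** The plan states no antibody incidence, subgroup size or expected difference, so there is no figure to reproduce.

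**Step 1. Samples per subject (Table 5-1; Protocol 8.2–8.10).** Post-Baseline PS0011 samples, SFU excluded:

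- Completer: Weeks 4, 8, 12, 16, 28, 40, 48 = 7.
- Failure at Week 12, withdrawn at that visit: 3, so 7/3 = 2.33.
- Failure at Week 12 with a separate Early Withdrawal visit: 4, so 7/4 = 1.75.
- Failure at Week 16: 4 or 5 samples, ratio 1.75 or 1.4. At Week 28: 5 or 6, ratio 1.4 or 1.17. At Week 40: 6 or 7, ratio 1.17 or 1.0.
- With the PS0011 Baseline sample added, Week 12 withdrawal at the same visit gives 8/4 = 2.0. With SFU added for both instead, 8/4 = 2.0 or 8/5 = 1.6.

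Samples from PS0010 also count towards the status and dilute the ratio. Their number is not in these documents.

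**Step 2. Gap at Week 48 with no true antibody effect.** Assumed inputs: chance h of turning positive per sample, fraction f withdrawn at Week 12, PASI90 of 85% in completers, s PS0010 samples.

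- Withdrawn subject ever positive: p_w = 1 − (1 − h)^(3+s), or exponent 4+s with the extra visit.
- Completer ever positive: p_c = 1 − (1 − h)^(7+s).
- Overall: P = f·p_w + (1 − f)·p_c.
- Response if positive: (1 − f)·p_c·0.85 / P. Response if negative: (1 − f)·(1 − p_c)·0.85 / (1 − P).

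Middle case, h = 6%, f = 25%, s = 3:

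- p_w = 1 − 0.94^6 = 31.0%; p_c = 1 − 0.94^10 = 46.1%; P = 0.25 × 0.310 + 0.75 × 0.461 = 42.4%.
- Positive: 0.75 × 0.461 × 0.85 / 0.424 = 69.4%. Negative: 0.75 × 0.539 × 0.85 / 0.576 = 59.6%. Gap +9.9 points before rounding.

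| Setting | 3 samples for failures | 4 samples for failures |
|---|---|---|
| Middle case | 69.4% vs 59.6%, +9.9 | 67.8% vs 60.7%, +7.1 |
| h 3–10%, f 15–35%, s 1 or 3 | +5.5 to +17.5 | +4.1 to +12.4 |
| Middle case, but f = 5% | +2.5 | +1.8 |
| Middle case, but 50% PASI90 in completers | +5.8 | +4.2 |

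If h is zero after Week 12, then p_w = p_c and the gap is 0.

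**Step 3. Can a real loss be hidden?** Assume 30% fail at Week 12 if positive by then and 20% if not, with 80% response in completers. The true contrast is 0.70 × 80% − 0.80 × 80% = 56% − 64% = −8 points. Take h = 5%, no PS0010 samples, 3 samples for failures:

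- Positive by Week 12: 1 − 0.95^3 = 14.3%. Completers first positive later: 0.857 × 0.80 × (1 − 0.95^4) = 12.7%.
- Ever positive: 0.80 × (0.70 × 0.143 + 0.127) / (0.143 + 0.127) = 67.3%.
- Never positive: 0.80 × 0.559 / (0.171 + 0.559) = 61.2%, where 0.559 = 0.857 × 0.80 × 0.95^4 and 0.171 = 0.857 × 0.20.
- The table shows +6.1 where the truth is −8.

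Over h = 2–20%, a true −8 shows as +5.0 to +14.3 with no PS0010 samples, and +0.9 to +9.8 with three. With zero or three PS0010 samples, a true −16 shows as −4.5 to +8.9.

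**The case against.** **Two stronger readings are tempting, and neither is supported.**

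- A reader might infer that completers have more than twice as many PS0011 samples as early failures. That holds only for withdrawal at the Week 12 visit itself with Baseline and SFU left out. Protocol 5.1 has PASI75 failures return for the Early Withdrawal assessments, which suggests a fourth sample, and later failures have lower ratios.
- A reader might infer that antibody-positive subjects look better by construction. They do so only if first positivity continues after Week 12. The documents say nothing on when subjects turn positive, and a large true effect can still show with the right sign.

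**The size is uncertain.** Every input in Step 2 other than the sample counts is assumed, and placing all withdrawals at Week 12 is the least favourable arrangement. SAP 10.1 also presents efficacy tables by PS0010/PS0011 treatment group separately by PS0010 Week 12 PASI90 status unless otherwise specified. Among entry responders, few may fail PASI75, and the gap is then small. This stands and limits the magnitude.

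**The weight is limited.** This is one descriptive split among twelve in a study with no inferential analyses. First positivity is tabulated by visit and individual results are listed, so timing could be recovered. This also stands, but readers will still compare the two percentages. The SAP already summarises TEAEs by timing of onset relative to antibody status; efficacy has no such counterpart.

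**Two obvious repairs fail.** Time-updated status (positive at or before each visit) gives the same groups as ever-positive at Week 48. A Week 12 landmark restricted to subjects still on treatment drops the Week 12 failures; in the Step 3 scenario both groups would then show 80%, turning −8 into 0.

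**Conclusion.** The point holds in a conditional form. The subgroup is defined by a post-baseline status whose chance of being reached depends on follow-up, and the PASI75 withdrawal rule with NRI ties follow-up to the outcome. If seroconversion continues after Week 12, the comparison favours antibody-positive subjects and can hide or reverse a moderate loss of efficacy. If it does not, the bias is nil.

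Under the stated assumptions the no-effect gap at Week 48 is about 4 to 18 points across both sample counts. In the middle case with 5% withdrawn it is about 2.5 points (1.8 with the extra sample). The documents cannot narrow this further. No primary result is affected, but the one planned efficacy table by antibody status can mislead.

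**What to change.** In SAP 4.7, define antibody status for the efficacy subgroup at a fixed landmark: either through PS0011 Baseline, or from samples up to and including the PS0011 Week 12 visit, not counting any later Early Withdrawal sample. Apply it to all FAS subjects. Keep Week 12 PASI75 failures in the denominator as NRI non-responders, and summarise PASI90 and IGA at visits after the landmark. If the ever-positive split is kept, label it as dependent on length of follow-up.

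With the Week 12 landmark, a Week 12 failure and a completer have the same number of samples. In the middle case both groups then show 0.75 × 85% = 63.75% and the no-effect gap is 0; the Step 3 scenario shows its true −8.

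Cost: a short change to SAP 4.7 and reprogramming, with no new samples. Fewer subjects are classed as positive, and later seroconverters count as negative. The Baseline option says little about subjects who were on placebo throughout PS0010, because they had not yet received bimekizumab. The Week 12 option leaves a small sampling difference for anyone who leaves before Week 12 for other reasons.

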14.2 General statistical considerations

No inferential statistical analyses are planned for this extension study. Instead, all variables will be presented using summary statistics. For categorical variables, counts and percentages will be displayed. For continuous variables, summary statistics will consist of the number of available observations, arithmetic mean, standard deviation, median, minimum, and maximum unless stated otherwise.

Because subjects entering PS0011 may or may not be continuing on the same dose as that received in PS0010, there are various combinations of treatment that could be received when considering both PS0010 and PS0011 together. For describing the summaries to be produced, treatment groups will be categorized as either the PS0011 treatment groups or PS0010/PS0011 treatment groups. These categorizations are outlined below.

PS0011 treatment groups

This refers to the study treatment assigned to the subject at the beginning of PS0011 and does not account for the treatment received in PS0010. The PS0011 treatment groups are as follows:

- Placebo
- Bimekizumab 64mg Q4W
- Bimekizumab 160mg Q4W
- Bimekizumab 320mg Q4W
- All Bimekizumab (optional – to be used only if specified)

PS0010/PS0011 treatment groups

This refers to the combination of the randomized treatment in PS0010 and the treatment assigned at the beginning of PS0011. Some groups have been combined where it is considered appropriate to do so. The PS0010/PS0011 treatment groups with descriptions are as follows:

- Placebo to Placebo – Subjects randomized to placebo in PS0010 who achieve PASI90 response at Week 12 of PS0010 and continue to receive placebo in PS0011.
- Placebo to Bimekizumab 160mg Q4W – Subjects randomized to placebo in PS0010 who do not achieve PASI90 response at Week 12 of PS0010 and are treated with bimekizumab 160mg Q4W in PS0011.
- Bimekizumab 64mg to Bimekizumab 64mg – Subjects randomized to bimekizumab 64mg Q4W in PS0010 who achieve PASI90 response at Week 12 of PS0010 and continue to receive bimekizumab 64mg Q4W in PS0011.
- Bimekizumab 64mg to Bimekizumab 160mg – Subjects randomized to bimekizumab 64mg Q4W in PS0010 who do not achieve PASI90 response at Week 12 of PS0010 and are treated with bimekizumab 160mg Q4W in PS0011.

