2.4 Determination of sample size

Up to 240 subjects are anticipated to enroll in PS0011. This number is based on the 240 subjects that are planned to be randomized in the feeder study, PS0010. The calculations to reach this sample size are outlined in the PS0010 protocol and SAP. As the primary objective of this study is to assess the long-term safety and tolerability of bimekizumab, the number of subjects anticipated is based on the number of subjects completing PS0010 and meeting eligibility requirements for PS0011.

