10 EFFICACY ANALYSES

10.1 Statistical analysis of the efficacy variables

Efficacy variables will be analyzed for all subjects in the FAS.

Also, summary tables of each endpoint by visit and treatment will be provided.

Unless otherwise specified, summary tables for efficacy endpoints by PS0010/PS0011 treatment group will present data separately by responder status (defined as PS0010 Week 12 PASI90 response).

Efficacy endpoints will also be listed.

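### The SAP's sparse-subgroup rule lets one small treatment group, most plausibly placebo, suppress a subgroup category for every other group

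*SAP*

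**What the plan says.** SAP 4.7 states that "Subgroup analyses will be performed on the secondary efficacy variables", which are PASI90 response and IGA response over time. It lists 12 factors. Eleven have two levels and BMI has three, so there are 11 × 2 + 3 = 25 categories. The summaries use the Full Analysis Set with non-responder imputation and are descriptive only.

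The sparse-data rule reads: "If there are less than 2 subjects in any subgroup category/treatment group, then that subgroup category will not be summarized". The only relief follows it: "If it is possible to collapse subgroups with more than 2 categories, then collapsing may be done", with the aim of reaching at least 2 subjects in each category and treatment group. Placebo is not exempted, and Section 4.7 does not say which treatment grouping the subgroup tables use.

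Placebo is a separate group in both groupings of SAP 3.6. Protocol 14.2 defines who is in it: "Subjects randomized to placebo in PS0010 who achieve PASI90 response at Week 12 of PS0010 and continue to receive placebo in PS0011". For the PS0010/PS0011 grouping, SAP 10.1 adds that "summary tables for efficacy endpoints by PS0010/PS0011 treatment group will present data separately by responder status". SAP 10.1.1.2 and 10.1.2.2 also plan PASI90 and IGA summaries by PS0011 group.

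**The concern.** The trigger is a single category-by-treatment cell, but the consequence falls on the whole category. The collapsing sentence fits that reading, since it seeks categories that are adequately filled in every treatment group. A small group can therefore remove results for larger groups in which the category is well populated.

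Placebo is the obvious candidate, because its members had to reach a 90% PASI improvement on placebo. If 2 of 40 did so and everyone entered PS0011, 240 − 2 = 238 subjects would be on bimekizumab, yet the 2 placebo subjects would decide which bimekizumab subgroup results appear in any table with a placebo column. At stake are the planned descriptions of how response varies by factors such as weight, prior biologic use and antibody status.

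**Working it through.** **No figure to reproduce.** The documents give no placebo group size and no placebo PASI90 rate. The only relevant number is the 240 in SAP 2.4: "This number is based on the 240 subjects that are planned to be randomized in the feeder study, PS0010".

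**Inputs**
- Placebo subjects in PS0010: Protocol 2.2.1 lists six regimens with equal allocation, so 240/6 = 40. The printed ratio has five terms, which would give 240/5 = 48.
- Placebo PASI90 rate p at Week 12: assumed, 1% to 15%.
- Category shares: assumed 50/50 for binary factors and one third for each BMI level, checked against 80/20 for binary factors.
- Every placebo responder is assumed to enter PS0011.

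**What follows from the placebo group size n alone**
- n = 1: no category can hold 2 placebo subjects, so all 25 are dropped.
- n = 2 or 3: no factor can have 2 subjects in each of two levels, so at most one level per factor survives, or 12 of 25.
- n = 4 or more: a binary factor can keep both levels, depending on the split.
- n = 0: all 25 are dropped if an empty group counts as having fewer than 2 subjects. The text does not say whether it does.

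**Expected loss.** A category with share s is dropped when Binomial(40, p × s) is 0 or 1. For p = 5%:
- Binary level, s = 0.5: 0.975^40 + 40 × 0.025 × 0.975^39 = 0.736.
- BMI level, s = 1/3: the same formula with p × s = 0.01667 gives 0.857.
- Average: (22 × 0.736 + 3 × 0.857)/25 = 0.750.

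In the table, ranges run across the 50/50 and 80/20 assumptions. The last column treats an empty placebo group as no trigger, so it subtracts P(n = 0).

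| Assumed p | Mean n | P(n = 0) | P(n = 1) | Categories lost, empty group triggers | Categories lost, empty group does not trigger |
|---|---|---|---|---|---|
| 1% | 0.4 | 0.669 | 0.270 | 98.0–98.4% | 31.1–31.5% |
| 2% | 0.8 | 0.446 | 0.364 | 93.2–94.3% | 48.7–49.7% |
| 5% | 2.0 | 0.129 | 0.271 | 74.5–75.0% | 61.7–62.2% |
| 7.5% | 3.0 | 0.044 | 0.143 | 57.6–60.7% | 53.2–56.2% |
| 10% | 4.0 | 0.015 | 0.066 | 42.5–50.0% | 41.0–48.5% |
| 15% | 6.0 | 0.002 | 0.011 | 21.3–35.6% | 21.2–35.5% |

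At 5%, with an empty group triggering, the loss is 78–79% if 36 placebo subjects are at risk and 68–69% if 48 are.

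**Which tables are exposed.** These figures apply only where a placebo column is present: tables by PS0011 group and the responder side of tables by PS0010/PS0011 group. SAP 10.1.1.2 and 10.1.2.2 list five non-responder groups, and Placebo to Placebo is not among them. Other small groups could trigger the rule there. As an illustration with assumed figures, if a non-responder group has 10 subjects and 10% are aged 65 or over, the chance of fewer than 2 such subjects is 0.9^10 + 10 × 0.1 × 0.9^9 = 0.74.

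**After a cell-level rule.** A placebo group of 0 or 1 loses only its own 25 cells: 25 of 100 with four PS0011 groups, or 25 of 200 with eight PS0010/PS0011 groups. No active-dose result is lost because of placebo.

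**The case against.** The strongest reply is that the phrase naming what is dropped could refer back to the category-by-treatment cell. One might also collapse levels simply to avoid blank cells. On that reading the SAP already does what is wanted. This reading is possible but strained: the sentence names the category as the thing omitted. A rule that two programmers could apply in opposite ways would need clarifying in any case.

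Second, the size rests on a rate that the documents do not give. This stands. It is also fair that, at the lowest rates, much of the loss comes from the case of no placebo entrants, where the rule may not apply.

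Third, a reader might infer that the plan will produce no bimekizumab subgroup results at all, or that the responder split creates placebo cells that are empty by definition. The documents support neither. Total loss needs at most one placebo entrant, which has probability 0.129 + 0.271 = 0.40 at a 5% rate and less at higher rates. The SAP's own lists leave Placebo to Placebo out of the non-responder groups, so if the rule is applied table by table, placebo cannot remove those results.

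Fourth, the tables are descriptive, Protocol 14.2 plans no inferential analyses, and SAP 3.1 and 10.1 provide listings, so the data remain available. This lowers the severity. It does not make the rule sound, because a subgroup table produced after being suppressed under the SAP would no longer be a pre-specified one.

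**Conclusion.** The concern holds as a minor defect in the SAP. As naturally read, the rule lets one sparse treatment group suppress a subgroup category for all groups, and the collapsing provision can help only BMI.

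In tables with a placebo column, the expected loss is more than half of the categories for assumed placebo PASI90 rates up to about 8% if an empty placebo group triggers the rule. If it does not, the loss is about 31% at a 1% rate, peaks at about 62% at 5% among the rates examined, and is 41–49% at 10%. These figures rest on 40 placebo subjects, full entry of responders and the assumed category shares. They are conditional illustrations, not predictions.

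The primary safety objective and the main efficacy tables are unaffected.

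**What to change.** Replace the suppression sentence in SAP 4.7 with: *Within a subgroup category, results are not shown for a treatment group with fewer than 2 subjects (the count is shown); the category is still summarized for all other treatment groups.* Add a sentence naming the treatment grouping used for the subgroup tables and, if it is PS0010/PS0011, whether they are split by responder status. The new wording also settles the empty-group question, since such a group shows a count of zero and affects nothing else.

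Leaving the Placebo to Placebo group out of the subgroup tables is optional and is not needed once the rule works at cell level.

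The cost is two SAP sentences and a small change to table programming. No new data are needed.
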